3.1.2.2 Treatment Period

From Visit 2 onward, all visits will be the same for all patients regardless of whether they were considered to be "naïve" or "non-naïve" at the time of screening.

During the treatment period, all patients will receive N-Acetyl-L-Leucine for 42 days (+7 days). **Visit 3** (Treatment 1) will occur at Day 28 (+7 days) of the treatment period and **Visit 4** (Treatment 2) will occur after the full 42 days (+7 days) of treatment.

3.1.2.3 Washout Period

A 42-day (+7 days) washout period will be performed following treatment with N-Acetyl-L-Leucine. **Visit 5** (Washout 1) will occur on Day 28 (+7 days) of the washout period and **Visit 6** (Washout 2) will occur after the full 42 days (+7 days) of washout.

3.1.2.4 Extension Phase

Patients who have participated in the study will be offered the opportunity to participate in a planned Extension Phase if the safety and tolerability during the 42-day (+7 days) treatment are considered to be acceptable by the Investigator for each specific patient, and the Investigator determines further treatment with IB1001 to be in the patient's interest. Provided the patient (or their legal representative on their behalf) subsequently consent to participate, the Extension Phase is planned to allow patients to have further access to IB1001 for one year.

Following a 6-week post Extension Phase treatment washout (Visit 10 of the Extension Phase), patients will have access to IB1001 for an additional one-year in the Extension Phase Treatment Period II.

See Appendix 6 for the Protocol for Extension Phase.

3.1.2.5 COVID-19 Modifications to the Original Study Schema

COVID-19 has significantly impacted study subjects' ability to attend study visits due to government-ordered lockdowns or the closure of state (domestic) and/or national borders. In addition, the issuance of site-specific policies limiting or halting the conduct of non-essential study visits, the conversion of study-sites into COVID-19 wards, and site staff not on duty or reassigned to other priorities at the hospitals have affected the feasibility of conducting study visits. Finally, considering NPC patients are already classified as a vulnerable patient population, patients may be self-isolating.

If, per the reasons above, in-person visits cannot be carried out in accordance with the schedule of events, the following departures from the original study schema are allowed:

3.1.2.5.1 Non-Essential In-Person Visits: Treatment Visit 3/ Washout Visit 5

- Visit 3 and Visit 5 are "interim" visits of the treatment and washout phases, respectively.
- The Sponsor's Medical Expert, Medical Monitor, the DSMB, Biostatistician and Principal Investigators consider that missing the in-person Visit 3 and / or Visit 5 would not compromise the safety of the patient or the integrity of the study, and that the patient could continue with medication (Visit 3) or the post-treatment washout phase (Visit 5) without attending the in-person Visit 3 and / or Visit 5. This risk assessment was based on the previously established safety profile of IB1001 (see Section 1), the observed very good tolerability shown to date in this ongoing, openlabel study, including that no related serious adverse reactions had been reported with IB1001 (in any ongoing trial), that these visits are not critical to the primary outcome assessment, and that the integrity of the clinical trial could be maintained if these visits were not performed due to COVID-19 restrictions.
- Therefore, in-person Visit 3 and Visit 5 have been classified as non-essential visits and may be skipped if they are not feasible to conduct in-person due to national, local, or site-specific restrictions, or necessary to safeguard the site staff, patients, and their families. If the in-person Visit 3 and / or Visit 5 is skipped, a remote visit should be conducted in lieu of the in-person visit (see Section 3.1.2.5.3 below).

3.1.2.5.2 Essential In-Person Visits: End of Treatment Visit 4/ Washout Visit 6

- Visit 4 and Visit 6 are the final visits of the treatment/washout phase (respectively)
- The Sponsor's Medical Expert, Medical Monitor, the DSMB, and each Principal Investigator determined that the in-person Visit 4 and Visit 6 are necessary visits needed to fully assess the safety of trial participants, the primary endpoint, and maintain the integrity of the clinical trial.
- However, it was determined (if they are not feasible to conduct in-person due to national, local, or site-specific restrictions, or necessary to safeguard the site staff, patients, and their families) postponing the in-person Visit 4 and/or Visit 6 would not compromise the safety of the patient, and that the patient could continue with medication / be dosed longer than the planned 42 days (+7 days) treatment period (Visit 4). This risk assessment was based on the previously established safety profile of IB1001 (see Section 1), the observed good tolerability shown to date in this ongoing, open-label study, including that no related serious adverse reactions had been reported with IB1001 (in any ongoing clinical trial), that the Extension Phase (including one-year treatment period with IB1001) had been approved in all countries, and that data collected from these postponed in-person Visit 4 and/or Visit 6 was acceptable for the purpose of assessing a true treatment-related effect.
- Therefore, Visit 4 and Visit 6 have been classified as essential study visits which may be postponed (if they are not feasible to conduct in-person due to national, local, or site-specific restrictions, or necessary to safeguard the site staff, patients, and their families) but cannot be skipped. If Visit 4 and / or Visit 6 is postponed, a remote visit should be conducted at the time of the original the in-person visit (see Section 3.1.2.5.3 below)

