6.2.5 Electrocardiograms (ECGs)

During the study, 12-lead ECGs will be performed approximately at the time points designated on the schedule of events (Appendix 3A for "naïve" patients and Appendix 3B for "non-naïve" patients). In addition, ECGs may be performed at other visits at the discretion of the Investigator if the findings from a previous ECG was clinically relevant.

The patient must be in a supine position in a rested and calm state for at least 5 minutes before ECG assessment is conducted. If the patient is unable to be in the supine position, the patient should be in the most recumbent position possible.

All ECGs should be performed in a standardized method prior to blood draws or other invasive procedures.

Each ECG must include the following measurements:

Corrected QT, and whether the ECG is Normal, Abnormal NCS (not clinically significant), or Abnormal CS (clinically significant) for the patient.

The Principal Investigator or designated site physician will review and sign all ECGs. Results must be summarized in writing and classified as normal; Abnormal NCS (not clinically significant), or Abnormal CS (clinically significant) for the patient. Intervals of the ECG will be recorded in the eCRF. Once signed, the original ECG tracing will be retained with the patient's source documents. At the request of the Sponsor, a copy of the original ECG will be made available.

Due to COVID-19, ECGs may not be able to be collected at the designated timepoints in the schedule of events (e.g. if visits are skipped and replaced by remote visits or postponed) or if qualified study team members/ appropriate equipment are not available/accessible. The Sponsor's Medical Expert, Medical Monitor, and DSMB deem the risk posed by ECGs not being collected at the designated timepoints is acceptable in the context of remote visits where study staff will enquire regarding the health and wellbeing of the patient and assess for adverse events. This decision was based on the nature of the drug, the available non-clinical and clinical data for N-Acetyl-L-Leucine and N-Acetyl-DL-Leucine (see Section 1), and the safety profile (no reports of cardiac issues, including QTc prolongation) observed in this ongoing, open-label study (and also in other ongoing trials with IB1001) to date. ECGs will be routinely collected at Visit 9 in the Extension Phase, allowing for further assessment of any cardiac effects.

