7.1.2 Baseline Visit (Visit 2)

Visit 2 (Baseline 2): Day 14 (+7 days) after Visit 1 (Baseline 1). The final day/ second assessment of the baseline period. The start of the treatment period.

- Reconfirm patient eligibility, including confirmation that prohibited medications have not been used since **Visit 1**
- Documentation of frequency of therapy (hours per week)
- Documentation of concomitant medication
- · Vital signs
- Spinocerebellar Ataxia Functional Index (SCAFI) + Video-Recording for Clinical Impression of Change in Severity (CI-CS) Anchor Tests (9HPT-D and 8MWT)
- Scale for Assessment and Rating of Ataxia (SARA)
- Quality of Life EQ-5D-5L for patients aged ≥18 years, EQ-5D-Y for patients aged
 18 years
- Modified Disability Rating Scale (mDRS)
- Clinical Global Impression of Severity (CGI-S) by physician
- Clinical Global Impression of Severity (CGI-S) by caregiver
- Clinical Global Impression of Severity (CGI-S) by patient if able
- Urinalysis (done at central lab)
- Urine by dipstick: pregnancy test for women of childbearing potential (done at site before first dose of study drug is taken)
- Urine test for N-Acetyl-D-Leucine (test done at PK lab)
- Blood draw for safety laboratory tests (done at central lab)
- Blood draw for sparse PK (done at PK lab)
- Documentation of adverse events
- Dispensing of trial drug + intake of study drug at site

7.1.3 *Treatment 1 (Visit 3)*

Visit 3 (Treatment 1) Day 28 (+7 days) of treatment period: First assessment of treatment period with N-Acetyl-L-Leucine.

- Return of trial drug and compliance check (if feasible)
- Documentation of frequency of therapy (hours per week)
- Documentation of concomitant medication
- Vital signs
- Spinocerebellar Ataxia Functional Index (SCAFI) + Video-Recording of Clinical Impression of Change in Severity (CI-CS) Anchor Tests (9HPT-D and 8MWT)
- Scale for Assessment and Rating of Ataxia (SARA)
- Quality of Life EQ-5D-5L for patients aged ≥18 years, EQ-5D-Y for patients aged <18 years
- Modified Disability Rating Scale (mDRS)
- Clinical Global Impression of Severity (CGI-S) by physician
- Clinical Global Impression of Severity (CGI-S) by caregiver
- Clinical Global Impression of Severity (CGI-S) by patient if able
- 12-lead ECG
- Urinalysis (done at central lab)
- Blood draw for safety laboratory tests (done at central lab)

- Blood draw for sparse PK (done at PK lab)
- Documentation of adverse events
- Dispensing of additional study drug if needed

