7.1.4 Treatment 2 (Visit 4)

Visit 4 (Treatment 2): Day 42 (+7 days) of treatment period: the final day/second assessment of treatment period with N-Acetyl-L-Leucine. The start of washout period.

- Return of trial drug and compliance check¹⁴
- Documentation of frequency of therapy (hours per week)
- Documentation of concomitant medication
- Vital signs
- Spinocerebellar Ataxia Functional Index (SCAFI) + Video-Recording of Clinical Impression of Change in Severity (CI-CS) Anchor Tests (9HPT-D and 8MWT)
- Scale for Assessment and Rating of Ataxia (SARA)
- Quality of Life EQ-5D-5L for patients aged ≥18 years, EQ-5D-Y for patients aged <18 years
- Modified Disability Rating Scale (mDRS)
- Clinical Global Impression of Severity (CGI-S) by physician
- Clinical Global Impression of Severity (CGI-S) by caregiver
- Clinical Global Impression of Severity (CGI-S) by patient if able
- Clinical Global Impression of Change (CGI-C) by physician based on Visit 2 to Visit 4
- Clinical Global Impression of Change (CGI-C) by caregiver based on Visit 2 to Visit 4
- Clinical Global Impression of Change (CGI-C) by patient if able based on Visit 2 to Visit 4
- Urinalysis (done at central lab)
- Urine by dipstick: pregnancy test for women of childbearing potential (done at site)
- Blood draw for safety laboratory tests (done at central lab)
- Blood draw for sparse PK (done at PK lab)
- Documentation of adverse events

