Appendix 3A – Schedule of Events for "Naïve" Patients

Patient information and informed consent process	X					X ¹⁹	
Inclusion / exclusion criteria	X	X				X ¹⁹	
Patient weight and height measurements	X						
Confirmation prohibited medications have not been used in the past 42 days	X	X ^{3,4}					
Classify patient as "Naïve" or "Non-naïve"	X						
Patient demographics (in accordance with local regulations)	X						
Relevant medical history	X						
60-Day drug history	X						
Documentation of therapy	X	X	X	X	X	X	X
Vital signs	X	X	X	X	X	X	X
12-lead electrocardiogram (ECG) ⁵	X		X		X		X
Urine test for N-Acetyl-D-Leucine ⁶	X^7	X			X	X	X
Blood safety laboratory tests ⁸	X	X	X	X	X	X	X
Follicle stimulating hormone serum ^{8, 9}	X						
Urinalysis ⁸	X	X	X	X	X	X	X
Urine by dipstick for pregnancy test ¹⁰		X		X		X	X

Period	Baselin	Baseline Period		ent Period	Wash-O	Early Term.	
Duration of the whole period	1 Day	2 Weeks	6 W	/eeks	6 W	eeks	1 Day
Visit number	Visit 1 ¹	Visit 2 ²	Visit 3	Visit 4	Visit 5	Visit 6 / EOS	ET
Name of the Visit	Screening/Bsl 1	Baseline 2	Treatment 1	Treatment 2	Washout 1	Washout 2	ET
Timeline (Days)	Day -14	Day 1, Start IMP	Day 28	Day 42	Day 70	Day 84	XX
Visit Window allowed	na	+7 days	+7 days	+7 days	+7 days	+ 7days	na
Blood sample for sparse PK ⁶	X	X	X	X	X	X	X
Quality of Life EQ-5D-5L for patients aged ≥18; EQ-5D-Y ¹¹ for children aged <18 years	X	X	X	X	X	X	X
Scale for Ataxia Rating (SARA)	X	X	X	X	X	X	X
Modified Disabling Rating Score (mDRS)	X	X	X	X	X	X	X
Niemann-Pick Disease type C Clinical Severity Scale (NPC-CSS)	X						
Scale for Spinocerebellar Ataxia Functional Index (SCAFI) ¹²	X	X	X	X	X	X	X
Cognitive assessment according to standard procedures of the clinical site	X						
Determination of CI-CS Primary Anchor Test (9HPT-D or 8MWT)	X						
Clinical Global Impression of Severity (CGI-S) by Physician	X	X	X	X	X	X	X
Clinical Global Impression of Severity (CGI-S) by Caregiver	X	X	X	X	X	X	X
Clinical Global Impression of Severity (CGI-S) by Patient¹³	X	X	X	X	X	X	X
Clinical Global Impression of Change (CGI-C) by Physician				X		X	X
Clinical Global Impression of Change (CGI-C) by Caregiver				X		X	X
Clinical Global Impression of Change (CGI-C) by Patient ¹³				Х		X	X

Period	Baselir	ne Period	Treatme	ent Period	Wash-O	Early Term.	
Duration of the whole period	1 Day	2 Weeks	6 W	6 Weeks		6 Weeks	

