8.10 Determination of Sample Size

Sample size is determined by the number of patients that move into this Extension Phase from the parent study. The expectation is that between 60% and 70% of patients will rollover into the extension period. With 20 out of 32 patients (62.5%) rolling over, the study will have 80% power to detect an improvement in the success rate to 31% compared to the null hypothesis value of 10%.

9 DATA HANDLING AND RECORD KEEPING – EXTENSION See Section 9 of Parent Study.	ON PHASE	
CONFIDENTIAL Version 7.0, 10 Oct 2022	Page 154 of 161	

10 QUALITY CONTROL AND QUALITY ASSURANCE – EX PHASE	TENSION		
See Section 10 of the Parent Study.			
CONFIDENTIAL Version 7.0, 10 Oct 2022	Page 155 of 161		

11 ETHICAL, LEGAL AND ADMINISTRATIVE ASPECTS – PHASE	EXTENSION		
See Section 11 of the Parent Study.			
see seemen 11 of the falence state).			
CONFIDENTIAL	Page 156 of 161		
Version 7.0, 10 Oct 2022			

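### A patient who skips Visit 3 under the COVID-19 rule can complete the Parent Study with no ECG on drug, and the named back-up at Extension Visit 9 does not reach patients who do not roll over

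*Protocol*

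**What the plan says.** Three parts of the Protocol and one part of the SAP bear on this.

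**COVID-19 rules.** Protocol 3.1.2.5.1 says that "in-person Visit 3 and Visit 5 have been classified as non-essential visits and may be skipped if they are not feasible to conduct in-person", with a remote contact in their place. The remote list in 3.1.2.5.3 does not name an ECG; it has only an open item for extra assessments that investigator and patient agree on. Protocol 3.1.2.5.2 treats the other two visits differently: "Visit 4 and Visit 6 have been classified as essential study visits which may be postponed", but they cannot be skipped. It says that these in-person visits "are necessary visits needed to fully assess the safety of trial participants".

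**Schedule.** The ECG rows of Appendices 3A and 3B mark Visits 1, 3 and 5 and the Early Termination (ET) visit, and nothing else. The visit lists agree. Visit 3 (7.1.3), described as "First assessment of treatment period with N-Acetyl-L-Leucine", includes an ECG. Visit 4 (7.1.4), described as "the final day/second assessment of treatment period with N-Acetyl-L-Leucine. The start of washout period", does not, and neither does Visit 6 (7.1.6).

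**Acknowledgement.** Protocol 6.2.5 says that ECGs may be missed when visits are skipped or postponed. It records that the Sponsor's Medical Expert, the Medical Monitor and the DSMB consider this risk acceptable, and adds: "ECGs will be routinely collected at Visit 9 in the Extension Phase, allowing for further assessment of any cardiac effects". On how many patients get that far, Appendix 6, 8.10 says: "The expectation is that between 60% and 70% of patients will rollover into the extension period".

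**Analysis.** SAP 5.7.4 summarises corrected QT and the normal/abnormal reading by protocol visit. ECGs taken outside the scheduled visits go into listings and stay out of the summaries.

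**The concern.** The scheduled post-baseline ECGs of a patient who completes the Parent Study sit on exactly the two visits that may be skipped. No other routine safety test is placed this way. Vital signs, blood safety tests and urinalysis are also scheduled at Visits 4 and 6, so they survive a skipped Visit 3 or 5.

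At stake is the measurement itself. Such a patient takes the drug for 42 (+7) days, or longer, because Protocol 5.3 continues dosing up to a postponed Visit 4, and no ECG is scheduled while on drug. A remote enquiry about wellbeing and adverse events cannot supply a QTc value. The SAP adds a second loss: if a site records an ECG at another visit because Visit 3 was skipped, the rule in 5.7.4 appears to keep it out of the on-treatment summary.

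**Working it through.** No figure in the plan needs reproducing here. The check is a comparison of passages, followed by a scaling calculation.

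**Step 1. Where ECGs are scheduled in the Parent Study** (Protocol Appendices 3A and 3B, 7.1, 3.1.2.5, 4.3)

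| Visit | Phase | ECG scheduled | In-person visit may be skipped |
|---|---|---|---|
| 1 | before treatment | yes | no such rule |
| 2 | before first dose | no | no such rule |
| 3 | on treatment | yes | yes |
| 4 | on treatment, last assessment | no | no, only postponed |
| 5 | washout | yes | yes |
| 6 | washout, last assessment | no | no, only postponed |
| ET | preferably 7 to 14 days after last dose | yes | applies only to early leavers |

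Scheduled on-treatment ECGs: 1 (Visit 3). With Visit 3 skipped: 0. With Visits 3 and 5 both skipped, a completer has no scheduled post-baseline ECG. The ET visit does not help, because completers do not have one and its preferred timing is off drug.

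**Step 2. Whether any text carries a missed ECG forward.** Protocol 6.2.5 permits ECGs at other visits at the investigator's discretion where an earlier ECG finding was clinically relevant. The ECG footnote in both schedules ties repeats to clinically significant results at Visit 3. Neither clearly covers a Visit 3 ECG that was never recorded.

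**Step 3. The back-up.** The Extension schedule has one ECG, at Visit 9A on Day 365, plus one at Extension ET. Visit 9A is on drug, since the last dose of treatment period I is taken at Visit 9B. A patient who skips Visit 3 and reaches Visit 9A therefore has one scheduled on-drug ECG, about a year into extension dosing. A patient who does not enter the Extension has none.

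**Step 4. Size.** Inputs: about 39 enrolled (Protocol 3.1.3) and 60% to 70% rollover (Appendix 6, 8.10), so 30% to 40% not rolling over. The plan's own example, 20 of 32, leaves 12/32 = 37.5%. The share *s* who skip Visit 3 is not in the documents, so it is varied, and skipping is assumed to be independent of rollover.

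- No scheduled on-treatment ECG in the Parent Study: 39 × *s*.
- No scheduled on-drug ECG in the whole trial: 39 × *s* × (0.30 to 0.40).

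| *s* (assumed) | Parent Study: 39 × *s* | Whole trial: 39 × *s* × (0.30 to 0.40) |
|---|---|---|
| 10% | 3.9 | 1.2 to 1.6 |
| 30% | 11.7 | 3.5 to 4.7 |
| 50% | 19.5 | 5.9 to 7.8 |

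On the base of 32 used in the rollover example, the 30% row becomes 32 × 0.30 × (0.30 to 0.40) = 2.9 to 3.8. Dropout before Visit 9 would raise the whole-trial counts. ECGs taken at discretion would lower them.

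**The case against.** The strongest reply is that this was disclosed and decided. Protocol 6.2.5 says that ECGs may be missed, names who accepted the risk, and gives the grounds: the nature of the drug, the non-clinical and clinical data, and the safety profile observed to date. That stands, and it would be wrong to call the gap an oversight. It does not close the gap, though. The specific back-up is Visit 9, and it is missing for patients who do not roll over. These may not be a random subset: under Protocol 3.1.2.4, entry to the Extension requires the investigator to find safety and tolerability acceptable, so patients with tolerability concerns are the least likely to reach Visit 9.

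Other routes exist. Protocol 10.4 allows visits at alternative locations, and Appendix 6, 6.4.5 allows discretionary Extension ECGs without a prior finding. Both can reduce the number affected; neither guarantees an on-drug ECG after a skipped Visit 3. Missing data and their COVID-19 cause are recorded (Protocol 9.5), and summaries show the number of patients observed (SAP 5.3). Those provisions show how many ECGs are absent at each visit, but do not directly identify patients with none at all.

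Two stronger readings should be resisted. A reader might infer that 3.1.2.5.2 contradicts the schedule because Visit 4 is kept for safety reasons yet has no ECG. Visit 4 does carry vital signs, blood and urine tests and adverse event review, so this is a tension to reconcile, not a contradiction. A reader might also infer that the QTc remark in 6.2.5 is unsupported. That remark reports what had been seen so far in this and other trials of the drug, and claims nothing about unmeasured patients.

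**Conclusion.** Following the plan as written can leave a patient with no ECG on drug in the Parent Study, and with no post-baseline ECG if Visits 3 and 5 are both skipped. For patients who do not enter the Extension, the back-up named in Protocol 6.2.5 does not apply.

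The whole-trial size is about 1 to 2, 4 to 5 or 6 to 8 patients at assumed skip shares of 10%, 30% and 50%, with 39 enrolled, 60% to 70% rollover, and skipping independent of rollover.

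A reader might infer that some patients definitely have no on-drug ECG, or that 12 to 16 patients are affected. The documents support neither. They show only that the loss can occur and do not report how many Visit 3 ECGs were missed. The range 39 × 0.30 = 11.7 to 39 × 0.40 = 15.6 counts patients not expected to roll over; it would equal the number affected only if every patient skipped Visit 3.

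One limit: Protocol 8.11 and SAP 8 refer to a COVID-19 addendum to the SAP that is not among the documents. It may address the analysis part of this point.

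**What to change.** **Protocol.** The sponsor should reconcile 3.1.2.5.1, 3.1.2.5.2, 6.2.5, the ECG rows of Appendices 3A and 3B, and the rollover expectation in Appendix 6, 8.10. The result should state how on-drug cardiac assessment is defined for a patient who skips Visit 3 and does not enter the Extension. What that assessment should be is for the sponsor's clinical team. Tying it to an in-person visit that already takes place would avoid adding a visit. Where Parent Study visits are already complete, only the SAP part can still change anything.

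**SAP 5.7.4.** Three changes:

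- Amend the rule that unscheduled ECGs are only listed. An ECG recorded on treatment at another visit because Visit 3 was skipped should enter the on-treatment summary, and likewise for Visit 5 and washout. The treatment and washout cycles already defined in SAP 5.7.1 can serve as the windows.
- Where the scheduled record exists, use it alone, so that no patient counts twice.
- Report the number of treated patients with no on-treatment ECG and the number with no post-baseline ECG.

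**Cost.** A few sentences in the SAP and two counts, with no new data for the reporting part. The downside is small: the timing of the on-treatment ECG becomes more mixed. Showing days on drug at the ECG in the listing would make that visible.
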